1.10 Exploratory Objectives

The exploratory objective is to pilot test integration of PRO data into the ED clinical workflow, specifically when PROs identify specific patient barriers that may be addressed by a follow-up call to help patients with the logistics of filling a prescription or scheduling a follow-up appointment. As part of regular ED clinical care at YNHH, we have a follow-up nurse that calls many patients post-ED discharge to facilitate follow-up and clinical care, yet there is no current mechanism for PROs to drive the content or timing of these follow-up calls. For the purposes of this study, the RA will deliver phone calls when participants have trouble filling a prescription or scheduling a

follow-up appointment, as determined by responses in Survey 2. As there is no control group for this study to be used as a comparison, the exploratory objective will simply be described based on our experience throughout the study.

STUDY DESIGN

1.11 Overview of Study Design

Overview:

The Hugo platform will deliver a link to survey in Hugo via email or text message to approximately 200 patients that have been registered as Hugo users by ED and/or research staff and enrolled in the study. Surveys will be delivered to participants at three separate timepoints (baseline, within one week and 30 days following enrollment).

Progression of study design:

As part of the study design, survey timing and content will be changed or updated periodically based on 1-2 month cycles of iterative testing (i.e., up to a total of 4 unique PROs will be delivered throughout the study period) to allow the research team to assess success of specific measures for a particular population and make survey response and patient contact data available to the research team to facilitate patient engagement and action. All questions will be derived from the list of potential PROs included as attachments (Baseline Survey, Survey 2, Survey 3) to this submission and timing of survey distribution may change based on feedback (i.e., 2-day survey may be delivered at 3 or 4 days, if more feasible or appropriate based on PROs delivered). Changes will not compromise the ability to measure outcomes previously described but will be implemented as necessary based on knowledge and experience throughout the study.

A sample timeline for iterative testing includes:

Iteration 1: May 1 – June 30, 2019
Iteration 2: July 1 – Aug 31, 2019
Iteration 3: Sept 1 – Oct 31, 2019
Iteration 4: Nov 1, 2019 – Dec 31, 2019

Sample iterations of PROs include:

Iteration 1:

Baseline survey: Delivered upon enrollment and includes contact information, overdose question, DSM-V criteria for OUD

Survey 2: Delivered 2 days post-enrollment (or 2 days post hospital discharge if the participant was admitted from the ED at enrollment) and includes review of ED care, linkage with treatment and prescriptions post-discharge, and changes in behavior (i.e., TEA assessment)

Survey 3: Delivered 30 days post-enrollment (or 30 days post hospital discharge if the participant was admitted from the ED at enrollment) and includes linkage with treatment and prescriptions, overdose history, and changes in behavior (i.e., TEA assessment)

Iteration 2:

Baseline survey: Same as above

Survey 2: Delivered 3 days post-enrollment (or 3 days post hospital discharge if the participant was admitted from the ED at enrollment) and includes information above, plus or minus certain questions and/or assessments from the list of potential PROs

Survey 3: Delivered 30 days post-enrollment (or 30 days post hospital discharge if the participant was admitted from the ED at enrollment) and includes information above, plus or minus certain questions and/or assessments from the list of potential PROs

Study Flow:

1. Upon enrollment, participants will be prompted to complete a baseline survey delivered via Hugo during their ED visit.
2. Participants will receive a follow-up survey via Hugo via email or text within one week of enrollment (or within one week of post hospital discharge if the participant was admitted from the ED at enrollment). If patients identify difficulties with obtaining a follow-up appointment or picking up medications, to test the ability to integrate PROs into our clinical workflow, patients may receive a follow-up call to assist with the logistics of obtaining a follow-up appointment or picking up medications. During this call, the RA will clarify issues related to medication pick-up or accessing treatment services if they are identified in the survey and will refer patient to follow-up nurse as needed. This call is not to provide counseling or treatment, or intended to provide an intervention.
3. Participants will receive a final survey within one month of enrollment.
4. If at any point participants fail to complete a survey, they will receive up to three email or text reminders and one phone call from the study RA to encourage survey completion. If no participant contact is elicited, the study RA will call the secondary contact person in an effort to locate the participant. Participants who fail to complete surveys within one month of initial follow-up survey receipt will be considered lost to follow-up.

Data Management:

A summary of survey data will be available 24/7 to researchers via the secure Hugo research dashboard. This data is updated in real-time and will be monitored weekly by a study RA to track survey completion, reminders and participants that are LTFU. Individual survey responses will be managed by Hugo and shared with study staff via secure file transfer every two weeks or as needed for analysis and development.

In addition, Hugo will automatically pull select data fields from each participant's shared records (EHR and pharmacy data) on a weekly basis. The infrastructure and agreements for secure data sharing between EHRs and pharmacies with Hugo are already established and occur automatically once patients link their accounts. Researchers will have access to data fields via Hugo for one year after enrollment for each participant and Hugo will send data fields to Yale via secure file transfer every two weeks or as needed. Access to data fields is permitted for one year to ensure that researchers have access to all participants data from the start of enrollment through analysis completion, should it be needed. Therefore, patients consent to sharing data for one year, although those enrolled later in the study will not be sharing data for the entire year. Survey, EHR and pharmacy data will be used to assess the study outcomes outlined above.

1.12 Duration of Study Schedule

Each subject will be actively on study until surveys are completed or until end of study eligibility period. Their passive participation in data sharing will last one year following enrollment.

OUTCOME MEASURES

1.13 Primary Outcome Measures

The primary outcome measures are the proportion of people who qualify for study criteria and enroll in the study, as well as response and follow-up rates among those who enroll.

1.14 Secondary Outcome Measures

PRO measures, such as patient experience, TEA assessment, and the proportion of participants receiving OUD medication and referral in the ED, enrolling in treatment and refilling prescriptions following their visit.

1.15 Other Outcome Measures

Proportion of patients who identify insurance, transportation barriers to filling follow-up prescription medications from the ED, and proportion of participants successful overcoming barriers after phone call.

1.16 Study Timeline

After receiving funder approval of the final protocol, Institutional Review Board (IRB) approval will then be obtained from the Yale University IRB. Once approved, enrollment will take place in the following year until up to 200 patients are enrolled or if the study enrollment time period ends per funding and program duration. Enrollment will be rolled out slowly, with an initial pilot period of up to one month. During this time, up to ten patients will be enrolled to ensure proper functionality of the Hugo tool, PRO delivery, EHR integration and data transfer. Their data will be included in the final data analysis.

Once all surveys and follow-up are complete for the study, EHR data collection will be finalized within two months of the final participant enrollment. Therefore, data lock is projected to occur approximately 12 months after IRB approval.

STUDY POPULATION

The study population consists of adult ED patients with OUD or non-medical opioid use, or those who are being treated for opioid overdose.

1.17 Participant Inclusion Criteria

Individuals must meet all of the following inclusion criteria in order to be eligible to participate in the study:

- Adult patient presenting to the YNHH YSC or SRC EDs
- History of opioid use disorder or non-medical use of opioids, as measured by screening assessment OR receiving treatment for opioid overdose
- Willingness and ability to complete electronic surveys via a smartphone or computer

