1.8 Primary Objective

The primary objective is feasibility testing to determine the proportion of ED patients with OUD, non-medical opioid use or overdose who are willing to share electronic health data with researchers and complete PROs delivered by a mobile-based technology platform. We hypothesize that patients will be willing to enroll and provide PROs both during and after discharge. The primary objective will be measured by the proportion of people who qualify for study criteria and enroll in the study by signing up for Hugo and sharing their EHR with researchers for this study, as well as response rates to electronic surveys and lost-to-follow-up (LTFU) rates among those who enroll. If successful, electronic PROs could offer an opportunity to improve follow-up and treatment among patients with OUD after discharge from the ED.

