1.26 Participant Reimbursement

Participants will receive up to \$30 for participation in this study. Payments will be made in the form of gift cards and include a \$10 payment after completion of enrollment, and each additional survey. Gift cards will be emailed to participants upon completion of each survey.

STUDY ASSESSMENTS

Study assessments are outlined below.

1. Quick Screen Form: To be used during baseline in-person interview prior to enrollment with any potentially eligible patient who is being screened for OUD or non-medical opioid use. It includes inclusion/exclusion criteria, brief questions about substance use and past 30-day opioid use, and a question about access to a smartphone or computer.
2. Baseline Survey: To be completed by participants electronically during their baseline visit after consenting, creating their Hugo account and sharing data with our study. Note that content of the baseline survey may change based on the iterations of the PROs outlined in this protocol and all questions will be derived from the list of potential PROs included with this protocol. It may include demographics, DSM-V criteria for OUD, and/or overdose history.
3. Survey 2: To be completed by participants electronically within one week of enrollment, or one week after hospital discharge if the participant is admitted from the ED at enrollment. Note that timing and content of survey 2 may change based on the iterations of the PROs outlined in this protocol and all questions will be derived from the list of potential PROs included with this protocol. It may include questions about patient experience during their initial ED visit, subsequent connection with treatment and prescriptions, overdose history, recent drug use, and overall health.
4. Survey 3: To be completed by participants electronically 30 days following enrollment, or 30 days after hospital discharge if the participant is admitted from the ED at enrollment. Note that content of survey 3 may change based on the iterations of the PROs outlined in the protocol and all questions will be derived from the list of PROs included with this protocol. It may include questions about connection with treatment and prescriptions, overdose history, recent drug use, and overall health.

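### Requiring willingness and ability to do electronic surveys for eligibility removes some unwilling or unable patients from the primary enrollment denominator, so the proportion is biased upward by an unknown amount

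*Protocol*

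**What the plan says.** Section 1.8 of the protocol sets the primary objective: to "determine the proportion of ED patients with OUD, non-medical opioid use or overdose who are willing to share electronic health data with researchers" and to "complete PROs delivered by a mobile-based technology platform". The population is described clinically. The Study Population statement just before section 1.17 names adult ED patients with opioid use disorder (OUD), non-medical opioid use or overdose and adds no condition on willingness.

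The measure is worded differently. Section 1.8 uses the "proportion of people who qualify for study criteria and enroll in the study by signing up for Hugo and sharing their EHR with researchers". Section 1.13 gives the primary outcome measures as "the proportion of people who qualify for study criteria and enroll in the study, as well as response and follow-up rates among those who enroll". The Statistical Design and Analyses section repeats this and names no other denominator.

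Section 1.17 requires every inclusion criterion to be met. The third is "Willingness and ability to complete electronic surveys via a smartphone or computer".

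Two collection tools bear on the point. The Quick Screen Form (Study Assessments, item 1) contains "a question about access to a smartphone or computer". The Screening Log (section 1.20.1) records refusals, reasons for being unable to take part, and the eligibility status of everyone approached. No section says how these records enter the primary proportion.

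**The concern.** In most studies a willingness criterion only limits generalisability. Here willingness is what the study sets out to estimate. Under the definitions as written, a patient with OUD who declines electronic surveys, or has no usable device, fails eligibility and disappears from the proportion when that patient should count against it.

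The boundary is also left to the research associate. A patient who says that they do not do surveys on a phone could be logged as failing the third criterion, and so leave the denominator, or as a refusal, and so stay in it. The protocol does not separate the two cases, so the primary proportion can move with coding alone.

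At stake is how the pilot's main result is read. An enrollment proportion among people already willing and able to do electronic surveys may be taken as an enrollment proportion among ED patients with the condition.

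**Working it through.** **The plan's own figure.** The only stated number is about 200 participants (section 1.3). It was chosen on feasibility grounds, so there is no formula to reproduce. No expected or target enrollment proportion is given, nor the share of patients likely to fail the third criterion.

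**Definitions**

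- T = approached patients who meet the age and opioid or overdose criteria and no exclusion (clinically eligible).
- f = share of T failing the willingness and ability criterion. Not in the documents; assumed 10% to 40%.
- Q = T(1-f) = those who qualify under section 1.17.
- E = enrolled, meaning signed up for Hugo and sharing the record (section 1.8). Nobody who fails the criterion can enroll, so E is the same under both denominators.

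**Formula.** The protocol measure is E/Q. The proportion among the clinically eligible is E/T. Since Q = T(1-f),

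E/Q = (E/T) × 1/(1-f).

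The measure is too high whenever f > 0 and equal only when f = 0. The direction follows from the definitions; the size depends wholly on f.

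**Forward illustration.** Assume T = 400 and E = 200, so E/T = 50%.

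| f (assumed) | Q | Reported E/Q | Factor |
|---|---|---|---|
| 10% | 360 | 200/360 = 55.6% | 1.11 |
| 20% | 320 | 200/320 = 62.5% | 1.25 |
| 25% | 300 | 200/300 = 66.7% | 1.33 |
| 40% | 240 | 200/240 = 83.3% | 1.67 |

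**Reverse illustration.** Suppose the study reports about 70%: 200/286 = 69.9%, Wilson 95% interval 64.4% to 75.0%.

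| f (assumed) | T = 286/(1-f) | E/T |
|---|---|---|
| 10% | 318 | 62.9% |
| 20% | 358 | 55.9% (95% interval 50.7% to 60.9%) |
| 30% | 409 | 48.9% |
| 40% | 477 | 41.9% |

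The overstatement in points is p × f, where p = E/Q. For assumed p of 50% to 90% and f of 10% to 40% it runs from 0.50 × 0.10 = 5 points to 0.90 × 0.40 = 36 points. At p = 70% and f = 20%, the 55.9% lies outside the interval around the reported figure, so sampling error would not cover the gap.

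**What stays in the denominator.** The third criterion concerns electronic surveys only. A patient who accepts surveys but declines consent, a Hugo account or record sharing still qualifies and counts as not enrolled. Unwillingness to share health data therefore remains measurable among those who accept surveys.

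**The case against.** **The denominator is not spelled out.** The outcome wording names no explicit base, so it could be read as qualifying and enrolling out of everyone approached, for whom the log exists. This reading is possible but less natural, and no section states it. A statistical analysis plan might settle the matter. The point is still more than missing detail, because the protocol fixes a measure in three places that, read plainly, does not match its objective.

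**The data are largely collected already.** This is true. It makes the repair cheap, but no section returns those failing the third criterion to the denominator.

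**The size is assumed.** This stands in full. Nothing in the documents supports 10%, 40% or any other value of f. The protocol screens for device access and plans help with email and portal accounts (section 1.22), which suggests that such barriers are expected, but it gives no rate.

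**A corrected denominator is still imperfect.** This also stands. It comes from a convenience sample, keeps the exclusions in section 1.18, and cannot place patients who refuse the verbal-consent screening, whose opioid status is then unknown unless they are being treated for overdose.

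**Stronger readings that the documents do not support.** A reader might infer that the primary outcome is wholly circular. It is not, because refusals of consent, Hugo or record sharing still count. A reader might also fault the response and loss-to-follow-up rates for being taken among enrollees. Those are ordinary feasibility measures, openly stated as such and valid for that group. Nor does anything require one composite primary outcome tied to Survey 3: the objective does not single out that survey, and a joint proportion follows from multiplying the stage rates once the first has the right base.

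**Conclusion.** The point holds in a limited form. As written, the primary enrollment proportion leaves out clinically eligible patients who are unwilling or unable to do electronic surveys, while the objective is about ED patients with the condition. The proportion is biased upward by 1/(1-f), which is 1.11 to 1.67 for an assumed f of 10% to 40%. This rests on the plain reading of the denominator and on at least one such patient being classed as ineligible.

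It would go too far to say that the feasibility conclusion will be materially wrong. The size of f is unknown, and this exploratory pilot has no success threshold, comparator or decision rule that an inflated proportion would trip. The sample size does not depend on it either. The definition should be corrected, but the mismatch does not undermine the study.

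**What to change.** Keep the third criterion in section 1.17 as a condition for enrolling, but take it out of the denominator. In section 1.13 and the Statistical Design and Analyses section, state something like:

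*The denominator of the primary enrollment proportion is all approached patients who meet the age and opioid or overdose criteria and no exclusion criterion. Patients who fail the electronic-survey criterion are counted as not enrolled and reported as (a) unwilling or (b) without a device or otherwise unable. Patients who refuse screening, so that opioid status is unknown, are reported separately.*

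Add two matching reason codes to the Screening Log and tell research associates how to apply them. Do this before enrollment starts: screening data are collected anonymously, so a reason not coded at the time may not be recoverable.

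Response and loss-to-follow-up rates among enrollees can stay as they are. The joint proportion that shared data and completed surveys, on the same denominator, may be added as a descriptive figure but need not be a new primary outcome.

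The cost is a few sentences, two log codes and a less favourable reported proportion. Eligibility, sample size and participant procedures do not change.

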1.18 Participant Exclusion Criteria

Individuals meeting any of the following exclusion criteria at baseline will be excluded from study:

- <18 years of age
- Inability to communicate in English
- Inability to provide consent (for example, due to psychosis, intoxication, severe mental illness, lack of capacity per clinician evaluation, or other reason)
- Awaiting emergent psychiatric evaluation

1.19 Strategies for Recruitment and Retention

Identification:

Participants will be identified in multiple ways, including:

- Electronic trackboard: The RA will continually monitor the ED trackboard for patients with a chief complaint of overdose or intoxication and conduct a brief EHR review for patients with these relevant chief complaints to assess inclusion/exclusion criteria. For patients that appear eligible, the RA will ask the treating ED clinician if the patient is currently clinically sober and meets inclusion and exclusion criteria to the best of the ED clinician's knowledge. The RA will then approach any patients that remain eligible. If a patient appears eligible but is currently intoxicated, he or she will be approached once the clinician deems them sober enough to have the capacity to consent to research.
- Referrals: All ED staff will be informed of our study and asked to refer patients when appropriate. Staff includes physicians, nurses, technicians and Project ASSERT staff. Project ASSERT is a YNHH ED service provided by health promotion advocates that connects patients with substance use disorders to treatment. ED staff will alert the RA of potential patients in person, by phone, email or Epic inbox.

Special Cases: It is possible that eligible patients screened in the ED may be admitted, in which case they will be followed to the inpatient floor if necessary to complete enrollment. Patients who are approached by research staff to participate, but decline participation, will not be re-approached during hospitalization, even if they were clinically intoxicated at the time they declined participation. It is also possible that participants enrolled in the ED could be on parole, which by definition qualifies as a prisoner in the state of Connecticut. For this reason, we will obtain OHRP Prisoner Certification to include individuals defined as prisoners by the state or federal regulations, which will be obtained prior to beginning enrollment. We do not plan to follow participants if incarcerated, however, as surveys are electronic and it is highly unlikely that prisoners would have access to a smartphone or computer while incarcerated. We will also not ask any questions at baseline or follow-up regarding parole or incarceration, given OHRP approval to include such participants.

Retention:

Participants will be compensated for the time to complete surveys, which should offset participant time as a barrier to follow-up survey completion. Participants who do not complete surveys within 24 hours of receipt will receive up to three email or text reminders (depending on their account preferences) and one reminder phone call as an attempt to obtain survey completion. Participants who fail to complete surveys within one month of initial receipt will be considered lost to follow-up.

SITE SELECTION

This is a single-site study conducted at the YNHH YSC and SRC EDs. The site was selected as it is the recipient of the study grant and capable of meeting all requirements related to patient population, staff, and resources.

STUDY PROCEDURES

